## 5.5 Sample Size Calculation

Sample size was reported in the original study protocol. Version G proposed an NIM of 4.7 points (based on an estimated baseline score distribution). With a sample size of 177 randomized subjects (118 A and 59 T), an effect size of -1.5 points, a standard deviation of 6 and a NIM of 4.7 points, the study has adequate power for the primary effectiveness endpoint. Power for the safety endpoint was also high assuming endpoint rates of 65% in T and 40% in A, including a 12% loss to follow-up rate.

## 5.6 Bayesian Predictive Probability Calculation

### 5.6.1 Overview

The study will include an interim predictive probability calculation. The calculation will take place after the 177th randomized patient is enrolled and treated. At this time point, it is estimated that 60 subjects will have 6-month data and 132 will have 3-month data, and 45 will have less than 3-

month data. The goal of the calculation is to determine the predictive probability of achieving non-inferiority and/or superiority for the primary safety and effectiveness endpoints at final analysis given all available trial data at the interim time point. The analysis will incorporate both observed data and predicted data.

If the predictive probability of non-inferiority for both the safety and effectiveness endpoints is  $\geq 0.99$ , a report summarizing primary and secondary endpoints will be submitted to FDA for consideration for device clearance. Primary endpoint claims from this submission would be based on non-inferiority only. PROCEPT will provide an update to FDA when all final data are available.

If the predictive probability of non-inferiority trial success is  $< 0.99$ , the trial will continue to the pre-planned sample size (177 randomized) and a single calculation (described in sections 5.1 and 5.2) performed when all study data are available.

Additionally, the predictive probability of superiority for the primary safety and effectiveness endpoints will be calculated. See the attached report from Berry Consultants for further details. In certain situations trial sample size may be increased to 300 randomized subjects with the goal of showing statistical superiority. This additional enrollment is for showing superiority only and will not affect FDA’s consideration of the device for market approval based on non-inferiority safety and effectiveness claims. It is expected that much of this additional enrollment, follow-up and analysis would take place in the post-market setting (i.e., after device clearance). Superiority claims will be based on a single final analysis when all data from all enrolled and treated subjects are available.

Interim Predictive Calculation

At the interim time point, we will calculate the Bayesian predictive probability of rejecting the safety and effectiveness non-inferiority hypotheses ( $H_{0,S,N}$  and  $H_{0,E,N}$ ) for 177 subjects so as to declare non-inferiority for the safety and effectiveness endpoints. We will use a similar approach to calculate the predictive probability of rejecting the safety and effectiveness superiority hypotheses ( $H_{0,S,S}$  and  $H_{0,E,S}$ ) for 177 as well as for total sample size of 300 subjects. Note that although interim calculations take a Bayesian approach, final calculations will be frequentist.

***Predictive Probability of Safety***

To calculate the predictive probability of non-inferiority or superiority, we use non-informative Jeffreys’ priors for the primary safety endpoints for the A and T groups:

$$S_A, S_T \sim \text{Beta}(\frac{1}{2}, \frac{1}{2})$$

Where Beta is the beta distribution. The posterior distributions are therefore:

$$S_A \sim \text{Beta}(\frac{1}{2} + X_A, \frac{1}{2} + N_A - X_A) \text{ and } S_T \sim \text{Beta}(\frac{1}{2} + X_T, \frac{1}{2} + N_T - X_T)$$

where  $X_A$  and  $X_T$  represent the number of safety events in the A and T groups, respectively, and  $N_A$  and  $N_T$  represent the number of A and T subjects, respectively with assessed 3-month safety outcomes.

The number of future successes is therefore calculated from a beta-binomial distribution. For the observed number of successes ( $X_A$  and  $X_T$ ) and every possible observed number of future successes ( $X_A'$  and  $X_T'$ ), we calculate the probability of each outcome  $\text{Pr}(X_A') \times \text{Pr}(X_T')$ , then determine if the combination  $(X_A + X_A') / (N_A + N_A')$  vs.  $(X_T + X_T') / (N_T + N_T')$  would produce a statistically significant result for the non-inferiority and superiority tests. Predictive probability is the sum of probabilities that result in positive trials, as described in Saville et al.

### ***Predictive Probability of Effectiveness***

At the time of the predictive probability calculation, some patients will have complete six-month outcome data (as well as 1- and 3-month data), some will have only 3-month data, some will have only 1-month data, and the most recently enrolled patients will not yet provide any efficacy data. Statistical models for predicting 1, 3 and 6-month IPSS scores, as well as a calculation of the predictive probability of effectiveness non-inferiority or superiority, are described in the attached report from Berry Consultants and not repeated here.

#### **5.6.2 Augmenting Enrollment for Superiority**

As noted above, predictive distributions will be calculated for 177 as well as for a total sample size of 300 subjects. For the superiority-focused calculations, there are 3 possible outcomes:

- Predicted probability of superiority for both outcomes with augmenting trial to 300 subjects size is low (<50%). In this case, the trial's sample size will NOT be increased. As noted above, a trial report will be sent to FDA, with an update when all subjects have 3-month safety and 6-month effectiveness data.
- Predicted probability of success at the interim sample size in both outcomes is high (>80%). As in the above scenario, the trial's sample size will NOT be increased and a trial report sent to FDA, along with the above-described update when 3- and 6-month safety and effectiveness data are available.
- Predicted probability of safety or effectiveness superiority after augmentation to 300 randomized subjects is between 50 and 80%. In this case, trial size will be increased to 300 subjects. If trial size is increased, it is expected that much of the follow-up phase and a single final analysis for these additional subjects will take place in the post-market setting when all data are available.

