4.4 Sample Size Considerations and Statistical Analyses

The WATER Study is designed as a prospective, randomized, blinded, controlled trial to demonstrate non-inferiority of the AQUABEAM System to TURP with respect to symptom improvement at 6 months. The WATER Study is designed in accordance with FDA's "Guidance for Non-Clinical and Clinical Investigation of Devices Used for the Treatment of Prostatic Hyperplasia (BPH)," published August 17, 2010.

Subjects will be randomly assigned in a 2:1 ratio to treatment with Aquablation or to treatment with TURP. The Primary Effectiveness Endpoint for this clinical trial is change in IPSS from baseline to 6-month evaluation.

Minimum enrollment (N_{\min}) in the WATER trial is 177 subjects (118 Aquablation and 59 TURP) to power at 80% for possible demonstration of superiority for the safety endpoint under an assumption of an endpoint rate of 65% in TURP and 40% in Aquablation, while including a 12% lost to follow-up rate (i.e., 156 evaluable subjects). The primary safety endpoint with 156 subjects evaluable displays over 99% power at a one-sided alpha level of 0.025 to demonstrate non-inferiority within a margin of 10% under an assumption of a true rate of events in the Aquablation group of 40% and expected rate of 65% in the TURP group.

Under an assumption of an effectiveness NIM of 4.7 points and a treatment effect of -1.5 points (i.e., mean change score in Aquablation is 1.5 points lower than TURP) with a standard deviation of 6 points, the sample size of 156 evaluable subjects provides more than 80% power in a test of non-inferiority for the primary effectiveness endpoint.

The trial will utilize a group sequential design with a single interim look and will incorporate a sample size re-estimation (SSR) at the time of the interim look based on promise for superiority on effectiveness. Methods for the SSR have been described in detail [30] [31].

An O'Brien-Fleming (OBF) alpha-spending function will be employed to control for type I error rate on the primary effectiveness endpoint. The maximum enrollment being considered is 270 total enrolled ($N_{\max} = 1.5$ times N_{\min}).

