An interim analysis incorporating a SSR will take place when all 177 subjects have been enrolled and completed the 3 month evaluation. The analysis will be performed by an independent statistician with a Data Monitoring Committee (DMC) review. Under the enrollment projection, it is assumed that 67% of the subjects will have completed the 6 month assessment at the time of the interim analysis. At this point, the non-inferiority test for primary effectiveness under an OBF alpha-spending function will be computed. Based on this result, the conditional power to claim superiority (CP_{sup}) on the primary effectiveness endpoint will also be computed. The conditional power (CP_{sup}) will be calculated based on the interim results of the primary effectiveness endpoint, with the specific interest of demonstrating superiority. CP_{sup} is defined as the approach that quantifies the statistical power to yield an answer different from that seen at the interim analysis. The data will be partitioned into three zones based on CP_{sup} unfavorable zone ($CP_{\text{sup}} < 40\%$), promising zone ($40\% \leq CP_{\text{sup}} < 80\%$), and favorable zone ($CP_{\text{sup}} \geq 80\%$). The following decision rules outline the possible outcomes of the interim analysis:

- (i) If the test for non-inferiority for primary effectiveness under an OBF alpha-spending function fails to reject the null hypothesis, there is no increase in sample size and the submission for the primary analysis will take place when all subjects have completed 6 months follow-up.
- (ii) If the test for non-inferiority for primary effectiveness under an OBF alpha-spending function rejects the null hypothesis, and if $CP_{\text{sup}} < 0.4$ or ≥ 0.8 , then there is no increase in the sample size and the study will be submitted to FDA based on the outcome from the interim analysis.

- (iii) If the test for non-inferiority for primary effectiveness under an OBF alpha-spending function rejects the null hypothesis, and if $0.4 \leq CP_{sup} < 0.8$, then the sample size will be increased by just the right amount such that CP_{sup} is increased to 0.8, under a cap of 270 subjects. The range $0.4 \leq CP_{sup} < 0.8$ is called the promising zone for superiority. Specifically, if CP_{sup} is in its promising zone, this decision rule increases the sample size by the smaller of 270 patients or the number needed to boost CP_{sup} to 0.8.

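### The protocol and the SAP give two incompatible interim adaptation and alpha plans, and neither says which one governs

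*SAP*

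**What the plan says.** Both documents start from 177 randomized subjects (118 Aquablation, 59 TURP). They part at the interim.

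| Element | Protocol 4.2-4.4 | SAP 5.1-5.3, 5.6 |
|---|---|---|
| Time point | "An interim analysis incorporating a SSR will take place when all 177 subjects have been enrolled and completed the 3 month evaluation"; "it is assumed that 67% of the subjects will have completed the 6 month assessment at the time of the interim analysis" | After the 177th subject is treated; "it is estimated that 60 subjects will have 6-month data and 132 will have 3-month data", and 45 have less |
| Interim test | Effectiveness non-inferiority, O'Brien-Fleming spending | None; Bayesian predictive probabilities only |
| Trigger for increase | Non-inferiority rejected and conditional power 40% to below 80%; this power "will be calculated based on the interim results of the primary effectiveness endpoint, with the specific interest of demonstrating superiority" | "Predicted probability of safety or effectiveness superiority after augmentation to 300 randomized subjects is between 50 and 80" percent |
| Size | As needed; "The maximum enrollment being considered is 270 total enrolled" | "In certain situations trial sample size may be increased to 300 randomized subjects with the goal of showing statistical superiority" |
| Early submission | Non-inferiority rejected and conditional power outside the zone; then "the study will be submitted to FDA based on the outcome from the interim analysis" | Predictive probability of non-inferiority at least 0.99 on both endpoints |
| Non-inferiority level | One-sided 0.025 overall, spent over two looks on effectiveness | Two-sided 95% interval, no adjustment |
| Safety superiority level | One-sided 0.025, no adjustment | Adjusted, by a method left to a separate document |

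On the last row the SAP is not consistent. Sections 5.1 and 5.2 call a superiority adjustment required because the sample size may increase. The same paragraphs name a (1-α)% interval for the superiority test and then declare superiority on the 95% interval. Section 5.3 adjusts only if enrolment is in fact enhanced.

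On precedence, protocol 4.4 leaves full statistical detail to the SAP. SAP section 1 sends the reader to the protocol for eligibility, treatments and assessments only.

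**The concern.** A superiority claim from an adaptive trial rests on the decision rule fixed in advance. Here the same trial could be enlarged under one document and not under the other, or submitted early under one and not the other. Its final tests would also be read at different levels. Someone checking a reported superiority result cannot tell from these documents which trigger, cap, time point and level applied.

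**Working it through.** **1. The shared base reproduces.** The protocol's inputs are 65% vs 40%, 2:1 allocation, 80% power, two-sided 0.05 and 12% loss. With continuity correction they give 52 + 104 = 156 evaluable (power 80.1%), and 156/0.88 = 177.3 against the stated 177. For effectiveness (margin 4.7, difference -1.5, SD 6), SE = 6√(1/104 + 1/52) = 1.019 and power is Φ(3.2/1.019 - 1.960) = 88.1%, consistent with the stated figure of more than 80%. The conflict is therefore not in the starting sample size.

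**2. Interim information.** Protocol 0.67; SAP 60/177 = 0.34.

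**3. Non-inferiority level.** The Lan-DeMets O'Brien-Fleming function at t = 0.67 spends 2[1 - Φ(2.241/√0.67)] = 0.0062, so the interim z is 2.502. The final z that keeps the total at 0.025, with correlation √0.67, is 1.994. That is one-sided 0.0231, or a 95.4% interval. The SAP's value is 1.960 (0.025, 95%). At 118/59, SE = 6√(1/118 + 1/59) = 0.957.
- Difference in the bound: (1.9936 - 1.9600) × 0.957 = 0.032 IPSS points.
- Power of the final test alone: Φ(3.2/0.957 - 1.960) = 91.7% against Φ(3.2/0.957 - 1.994) = 91.2%.

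**4. Enrolment decision under the protocol.** Current-trend conditional power at t = 0.67 is Φ[(d/0.957 - 1.994)/√0.33], where d is the observed IPSS difference in favour of Aquablation. It lies in 0.40-0.80 when d is between (1.994 - 0.253 × 0.574) × 0.957 = 1.77 and (1.994 + 0.842 × 0.574) × 0.957 = 2.37. Non-inferiority is then always rejected. With 79/40 subjects (67% of 177), the interim SE is 6√(1/79 + 1/40) = 1.164. At a true difference of -1.5 the chance is Φ(3.87/1.164) - Φ(3.27/1.164), about 0.2%.

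**5. Enrolment decision under the SAP.** This was simulated with these inputs:
- Safety: 40% vs 65%, 88/44 subjects observed, Jeffreys beta-binomial prediction as in the SAP, pooled z with and without continuity correction, final sizes 118/59 and 200/100.
- Effectiveness: flat-prior normal prediction, SD 6, from 40/20 subjects, or 66/34 to mimic information from 3-month scores.
- One-sided superiority level at 300 varied from 0.0125 to 0.025.
- If the second and third outcomes both held, the result was counted as no increase.

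| True IPSS difference | SAP increases | Protocol increases | Rules disagree |
|---|---|---|---|
| -1.5 (planning) | 14-19% | 0.2% | 14-19% |
| 0 | 21-27% | 4-5% | 20-27% |

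At the planning values 80-97% of the SAP-only increases come from safety alone.

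**6. Early submission at the planning values, margin 4.7 in both.** The protocol rejects with probability Φ(3.2/1.164 - 2.502) = 59.7%, almost always with conditional power outside the zone. For the SAP, from 40/20 subjects the variances are 36(1/40 + 1/20) = 2.70 now and 0.915 at the end. A predictive probability of 0.99 then needs d of at least 2.326√(2.70 - 0.915) - (4.7 - 1.96 × 0.957) = 0.28, which has chance 1 - Φ(1.78/1.643) = 14%. With the 66/34 assumption it is about 32%. Adding the safety condition gives about 11-27%.

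**7. Side note on SAP 5.6.2.** Its three outcomes are not exhaustive. Safety events of 35/88 vs 26/44 give a predictive probability of 0.78 at 177 and 0.86 at 300 (level 0.025, no continuity correction). If effectiveness at 300 is below 50%, no outcome applies. At level 0.0125 the value at 300 is 0.79 and the case falls inside the augmentation zone, so the gap depends on a level not supplied.

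**The case against.** The strongest reply is that the SAP governs in practice. The protocol delegates statistical detail to it. The SAP refers to version G in the past tense and responds to FDA feedback of August 2016. Rev. H is a post-market follow-up version that marks the endpoints as already reported, so its interim text may simply have been carried over. This is plausible, but it is inference. Replacing a trigger, a cap, a time point and a spending plan is more than detail, and Rev. H, dated 2020, still states its own rule as current text.

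The reply that the consequences are limited does stand. Up to 181 treated subjects suggests that no increase took place, the non-inferiority levels are close, and non-inferiority success does not depend on augmentation.

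A reader might infer three stronger things that the documents do not support:
- **The type I error is inflated.** Pairing the protocol's interim test with the SAP's 95% interval would give 0.0268, but neither document plans that pairing. If only predictive probabilities were computed, the 95% interval for non-inferiority needs no adjustment.
- **Each alpha plan is at least sound when read alone.** The SAP's is not, because 5.1-5.2 and 5.3 disagree on superiority.
- **The gap in 5.6.2 is a major flaw.** The pre-planned 177 is a natural default, and the consultant report and adjustment document, neither supplied, may close the gap.

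**Conclusion.** The two documents conflict on trigger, size, timing, early submission and alpha, with no statement of precedence. The SAP also conflicts with itself on the superiority level. These findings come from the text and need no model.

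At the planning values the enrolment rules disagree in about 14-19% of interims. That range rests on an assumed effectiveness model and an assumed superiority level at 300; it persists across the levels tried. The non-inferiority consequence is small: 0.0231 against 0.025, about 0.03 IPSS points or half a percentage point of power. What remains open is which rule and level any superiority claim should be read against. This should be fixed, but it does not put the non-inferiority conclusion in doubt.

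**What to change.** State in both documents which rule governed and was applied at the interim (trigger, cap, time point and submission criterion), and mark the other as superseded. Do not redesign the zones now that results are known.

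State one effectiveness non-inferiority level that matches what was done: about a 95.4% interval if the O'Brien-Fleming test was carried out at 67% information, or 95% if only predictive probabilities were computed. State one superiority level per endpoint, correct SAP 5.1-5.3 to agree with it, and base any superiority claim on that rule and level.

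For 5.6.2, record that results meeting none of the three outcomes stayed at 177, or cite the consultant report's rule.

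The cost is wording and a record of the rule applied, with possibly a slightly wider non-inferiority interval. No patients are added and no enrolment decision changes.

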## **6 Secondary Endpoint Assessments**

Six secondary endpoints, described below, are intended for marketing claims: 3 are based on 6-month results and 3 are based on perioperative results. Statistical testing for the 6-month secondary endpoints will only occur after data collection is complete.

Tests based on 6-month data:

1. Reoperation or re-intervention within 6 months. Reoperation means any surgical procedure on the lower urinary tract to treat problems potentially related to BPH. Re-intervention means any invasive procedure (e.g., cystoscopy) to evaluate problems potentially related to BPH. Re-intervention excludes TRUS and urodynamics, which are required study evaluations during follow-up. Re-intervention also excludes catheterization (which is not a surgical procedure) for acute urinary retention. The proportion of subjects with this endpoint will be compared using Fisher's exact test. Differences in proportions will be calculated with `testbinomial` from the `gsDesign` package. A 10% non-inferiority hypothesis (like the primary safety endpoint, of which this is a component) will be used and superiority will be explored after non-inferiority is shown.
2. The proportion of sexually active subjects reporting a worsening of sexual function through 6 months on either the IIEF or the MSHQ-EjD questionnaires. A subject is counted as having worse sexual function if IIEF-5 (part of IIEF-15) is decreased by at least 6 points or MSHQ is decreased by at least 2 points. The two-point threshold for MSHQ is close to

the value that distinguishes affected from unaffected men.\* Both IIEF and MSHQ assume that a man is sexually active. If the subject reports that he is not sexually active for the time period assessed, these threshold decreases cannot be met by definition. Differences in proportions will be calculated as described above. Superiority will be tested.

3. The proportion of subjects with major adverse urologic events (MAUE). MAUE is defined as any subject with a serious device- or serious procedure-related AE judged to be urologic through 6 months. Whether an event meets this endpoint is judged using the study's SAE definition and relatedness, both of which are adjudicated by the CEC. Differences in proportions will be calculated as described above. A 10% non-inferiority hypothesis (like the primary safety endpoint) will be used.

Tests based on perioperative data:

4. Length of hospital stay (days) in the treatment groups. Proportional odds logistic regression will be used. A NIM of ½ a day will be used. Additional analyses will be done stratifying for geography (e.g., Europe vs. US vs. Australia/New Zealand), as it is known that LOS is generally shorter in the US.
5. Length of operative time (minutes) in the treatment groups, defined as time from pre-treatment visualization to insertion of indwelling catheter (IDC), will be compared using a t test. Simple superiority will be tested.
6. Length of resection time (minutes) in the treatment groups, defined as start of first pedal activation to end of last pedal use for either A or T, will be compared using a t test. Simple statistical superiority will be evaluated.

The 6 endpoints listed above will be tested in sequential fashion using the Holm step-down procedure for type-I error rate correction. The testing will be done only if the primary safety and effectiveness endpoints meet the study's non-inferiority goals. Secondary endpoints listed above will be ordered sequentially from most significant to least significant. The endpoints will then be tested in order at adjusted levels of significance (i.e. E1: 0.05/k, E2: 0.05/k-1; E3: 0.05/k-2, etc., where k=number of specified endpoints). Once an endpoint fails, all subsequent secondary endpoints will not be statistically tested.

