4.6 Additional Endpoints

The following secondary objectives are intended to support product labeling. The endpoints will be tested in sequential fashion using the Holms step-down procedure for type-I error rate correction if and only if the primary objective passes according to the non-inferiority criteria outlined above. At the conclusion of the trial, the secondary endpoints intended for product labeling will be ordered sequentially from most significant to least significant. The endpoints will then be tested in order at adjusted levels of significance (i.e. E1: 0.05/k, E2: 0.05/k-1; E3: 0.05/k-2; E4: 0.05/k-3; E5: 0.05/k-4;, where k=number of specified endpoints). Once an endpoint fails, all following endpoints will not be tested. Following is a list of secondary endpoints intended to support product labeling:

- Evaluation of the proportion of subjects requiring re-operation and re-intervention through 6 months. The following hypothesis will be tested:

$$H: P_C - P_T > -\delta$$

where P_T and P_C represent proportions of subjects requiring re-operation or re-intervention through 6 months post treatment. The Aquablation group will be declared to be non-inferior to TURP if it can be established that the difference is within the non-inferiority margin of $\delta = 0.10$. The statistical test will be a z-test using pooled variance estimate and no continuity correction. In the case of small counts, an exact procedure will be used. Descriptive statistics and 95% confidence intervals will be calculated.

- Evaluation of the proportion of sexually active subjects reporting a worsening of sexual function through 6 months defined as a decrease of 6 points or more on the IIEF-5 (part of the IIEF-15) or a decrease of 2 points or more on the MSHQ-EjD questionnaires. The following hypothesis will be tested:

$$H_0: P_T = P_C$$

$$H_a: P_T < P_C$$

where P_T and P_C represent proportions of subjects with worsening score on the IIEF-5 and/or the MSHQ-EjD from baseline through 6 months post treatment. The statistical test for superiority will be a z-test using pooled variance estimate and no continuity correction. In the case of small counts, an exact procedure will be used. Descriptive statistics and 95% confidence intervals will be calculated.

- Evaluation of the mean length of hospital stay in the treatment groups. The following hypothesis will be tested:

$$H: \mu_T - \mu_C > 0$$

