where μ_T and μ_C is the average length of stay in days in the treatment and control groups, respectively. Statistical summaries will include means, medians, and standard deviation, as well as 95% confidence intervals. A t-test for superiority will be performed to test the hypothesis that μ_T is significantly less than μ_C .

- Evaluation of the mean length of operative time in the treatment groups. The following hypothesis will be tested:

$$H: \mu_T - \mu_C > 0$$

where μ_T and μ_C is the average operative time in minutes in the treatment and control groups, respectively. Statistical summaries will include means, medians, and standard deviation, as well as 95% confidence intervals. A t-test for superiority will be performed to test the hypothesis that μ_T is significantly less than μ_C .

- Evaluation of the mean length of resection time in the treatment groups. The following hypothesis will be tested:

$$H: \mu_T - \mu_C > 0$$

where μ_T and μ_C is the average operative time in minutes in the treatment and control groups, respectively. Statistical summaries will include means, medians, and standard deviation, as well as 95% confidence intervals. A t-test for superiority will be performed to test the hypothesis that μ_T is significantly less than μ_C .

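### Length of stay, a labelling endpoint: the protocol plans a superiority t-test on mean days, while the SAP plans a half-day non-inferiority margin on a proportional odds model and gives no rule for applying it

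*SAP*

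**What the plan says.** Protocol 4.6 lists length of stay among the secondary endpoints that support labelling. The objective is "Evaluation of the mean length of hospital stay in the treatment groups". Each mean "is the average length of stay in days in the treatment and control groups, respectively". The analysis is stated as "A t-test for superiority will be performed to test the hypothesis that" the Aquablation mean is below the TURP mean. There is no margin.

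SAP section 6 opens: "Six secondary endpoints, described below, are intended for marketing claims". Item 4 is length of stay: "Proportional odds logistic regression will be used. A NIM of ½ a day will be used". It adds analyses stratified by geography, because "it is known that LOS is generally shorter in the US". It mentions no superiority test. Item 1 (reoperation) does add that "superiority will be explored after non-inferiority is shown"; items 2, 5 and 6 are superiority tests; item 3 (major adverse urologic events) is non-inferiority only.

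Both documents rank these endpoints under Holm, starting at 0.05/k. The SAP closes with the rule: "Once an endpoint fails, all subsequent secondary endpoints will not be statistically tested".

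Three other places matter. SAP section 7, item 3, uses the same half-day margin for catheter duration, with a t test. Protocol 4.4 leaves full statistical detail to the SAP. Protocol 3.3, which lists length of stay, is marked as already reported.

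**The concern.** There are two separate problems.

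- **The hypothesis differs.** Superiority on mean days and non-inferiority within half a day license different label statements: a shorter stay, or a stay less than half a day longer. Operative time and resection time remain superiority t tests in both documents, so the difference is specific to length of stay. Neither document explains it.
- **The SAP's margin has no stated link to its model.** A proportional odds model estimates a common odds ratio. The SAP gives no odds-ratio margin, no conversion and no model-derived difference in days. Two analysts following item 4 could compare different quantities with half a day and reach different answers.

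At stake are one label claim and, through the Holm ranking, the significance levels applied to the other five endpoints.

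**Working it through.** The documents state no power, SD or expected value for length of stay, so there is no planned figure to reproduce. Every SD and stay distribution below is an assumption.

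**1. The two plans side by side**

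| | Protocol 4.6 | SAP 6, item 4 |
|---|---|---|
| Quantity | mean days per arm | odds ratio (days appear only in the margin) |
| Method | t-test | proportional odds logistic regression |
| Hypothesis | superiority | non-inferiority, half a day |
| Superiority step | yes | none stated |

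**2. What odds ratio equals half a day?** For stays of 1 to 5 days, mean = 5 − Σ P(stay ≤ j), j = 1 to 4. Under proportional odds, an odds ratio OR for longer stay divides the odds of each P(stay ≤ j) by OR.

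- Shorter-stay setting, control shares 0.80/0.15/0.03/0.01/0.01. The cumulative values sum to 3.72, so the mean is 1.28. With OR = 3.93 they become 0.504, 0.829, 0.926, 0.962 (sum 3.221), so the mean is 1.78, which is +0.50 day.
- Longer-stay setting, control shares 0.15/0.35/0.30/0.15/0.05. The cumulative values sum to 2.40, so the mean is 2.60. With OR = 2.30 they become 0.071, 0.303, 0.635, 0.892 (sum 1.901), so the mean is 3.10, which is +0.50 day.
- Swapping the two: OR 2.30 in the shorter-stay setting is only +0.26 day, and OR 3.93 in the longer-stay setting is +0.82 day.

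Four further assumed shapes gave odds ratios from 2.04 (0 to 5 days: 5/30/30/20/10/5%) to 7.29 (0 to 3 days: 5/85/8/2%). The equivalence depends on the stay distribution, so the margin needs a stated rule.

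**3. How far apart can the two hypotheses be?** This is an illustration with both tests placed on mean days, true difference 0 and 118/59 subjects (protocol 4.4).

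SE = SD × √(1/118 + 1/59) = SD × 0.1594. P(non-inferiority passes) = Φ(0.5/SE − z).

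| Assumed SD (days) | 0.5/SE | One-sided 0.025 (z 1.960) | Strictest Holm step, 0.05/6 two-sided (z 2.638) |
|---|---|---|---|
| 0.5 | 6.27 | 1.000 | 0.9999 |
| 1 | 3.14 | 0.880 | 0.691 |
| 2 | 1.57 | 0.347 | 0.142 |

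Superiority with equal stays passes at the test level: 0.025, or 0.0042 at the strictest step. If 0.05/6 is applied to a one-sided p-value instead (z 2.394), the non-inferiority figures are 0.9999, 0.771 and 0.204. SAP section 6 does not say which applies.

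At SD 1, non-inferiority passes for an observed Aquablation-minus-TURP difference up to 0.5 − 1.960 × 0.1594 = +0.19 day. Superiority needs −1.960 × 0.1594 = −0.31 day or less. Between these values the two tests disagree.

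**4. Holm, k = 6 (SAP).** If length of stay ranks first and passes, the other five face 0.05/5 down to 0.05/1. If it ranks last, they face 0.05/6 down to 0.05/2. At these extremes the weakest other endpoint is tested at 0.05 or at 0.025.

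**The case against.** **The protocol defers detail to the SAP.** That can cover the choice of model. It does not cover a move from superiority to non-inferiority on an endpoint meant for the label.

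**The odds model and the margin can be reconciled.** This stands in part. A reader might infer that a margin in days can never be used with a proportional odds model. That is too strong: the fitted category probabilities yield a mean difference in days. The supported point is that the SAP specifies no such step. The planned analyses by geography are additional and do not supply one.

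**Superiority implies the half-day result, so nothing is lost.** This holds only if both tests use mean days, and even then not in reverse. A reader might extend it to the SAP's test as written. The documents do not support that, because the t-test and the odds model weight long stays differently and the SAP's comparison quantity is not defined.

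**The numbers are assumed, and the contrast is built in.** This stands. With equal stays, superiority passes at its level by construction and any positive margin passes more often. The range of 35% to 100% shows that the choice can matter, not how much it mattered here. Nor does either document plan the mean-days non-inferiority test for length of stay. The conflict and the missing rule do not depend on these figures.

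**The Holm effect is limited.** This also stands. For the weakest other endpoint it changes the result only if that p-value lies between 0.025 and 0.05, and only at the extreme ranks.

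**Conclusion.** The concern holds. Protocol 4.6 and SAP section 6, item 4, set different hypotheses for length of stay, and the SAP does not say how its half-day margin is applied. Both follow from the text alone. The odds ratios and pass rates are illustrations that rest on assumed stay distributions and SDs.

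This should be fixed, but its reach is one secondary endpoint and, through Holm, possibly the levels for the other five. The primary endpoints, the sample size and the stated non-inferiority power are unaffected. A reader might infer that the reported length-of-stay result is wrong, or that the easier test was chosen after the data were seen. The documents do not show which hypothesis was fixed first or which was used, so neither inference is supported.

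**What to change.** 1. Check the reported length-of-stay analysis against the dated plan versions. Disclose which hypothesis and method were prespecified and which were used.
2. Then state one hypothesis identically in SAP section 6, item 4, and protocol 4.6. Make this a dated clarification, labelled post hoc where that applies, not a silent alignment.
3. Apply any half-day margin to the Aquablation-minus-TURP difference in mean days with its confidence interval, in line with SAP section 7, item 3. Alternatively, specify exactly how a mean difference in days and its interval are derived from the odds model.
4. State which p-value enters Holm and whether it is one- or two-sided.
5. Base any claim of shorter stay only on a superiority test.

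Editorial only: in protocol 4.2, change the bracket after the superiority statement to μ_T < μ_C, to agree with the section's own sign convention. In protocol 4.6, print μ_T − μ_C < 0 for the three time endpoints, to agree with the sentence after each, and define the third as average resection time.

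Cost: one check against dated versions, one aligned paragraph in each document and a few symbol corrections. No new data are needed.
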